9.2 Informed Consent and Enrollment Procedures

If a patient is deemed eligible and is willing to participate in the study, the investigator or designated member of the study staff will properly obtain a written informed consent form (ICF) from the patient prior to study enrollment. The ICF and any revisions must have prior approval of the study site's institutional review board (IRB) or equivalent (eg, ethics committee [EC] or ethics board [EB]).

Patients who sign the informed consent form will be considered enrolled in the study. A sample ICF for this study is provided in a separate document. No patient should undergo any study-specific tests or exams that fall outside the standard of care without first signing the informed consent document for this study. After signing the study's ICF, enrolled subjects will undergo further AF monitoring to confirm freedom from arrhythmia recurrence. Subjects who are deemed free from arrhythmia recurrence and qualify for enrollment according to the study inclusion and exclusion criteria will be randomized to one of the two study arms and followed through the Evaluation Period (12 months).

Figure 1.0 Study Flow Chart

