9.6 Subject Disposition

Evaluable Subjects

- **Enrolled Subjects:** subjects who sign the study's informed consent form
- **Randomized Subjects:** subject who remain free from arrhythmia recurrence after signing the study ICF and are randomized into one of the study arms (OAT withdrawal or OAT).
- **Completed Subjects:** enrolled subjects who have not been discontinued, withdrawn or lost-to-follow-up from the study prior to the final (12 month) study visit.
- **Lost to Follow-up Subjects:** subjects who are enrolled and randomized, but contact is lost after most recent follow-up visit (despite 3 documented attempts to contact the subject, two (2) by documented telephone calls, and one (1) written attempt sent by registered mail).
- **Discontinued:** Subjects that have arrhythmia recurrence at any time during the Evaluation Period will be discontinued. Discontinued subjects are exited from the study prior to completion of all follow-up visits; however, they will remain in the analysis cohort until the time at which they are discontinued from the study.
- **Withdrawn Subjects:** Subjects may be withdrawn for reasons stated below in Section 9.7. Withdrawn subjects are exited from the study prior to completion of all follow-up visits; however, they will remain in the analysis cohort until the time at which they are withdrawn.

Non-Evaluable Subjects

- **Excluded:** Subjects found to not meet one of the study inclusion/exclusion criteria after the being enrolled.

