13.4 Analysis Population

The study contains two treatment arms with subjects either discontinuing OAT or continuing OAT. The primary analysis will be based on the intent-to-treat principle where subjects will be analyzed by the group to which they are randomized, regardless of actual treatment received. Lost-to-follow-up, discontinued, and withdrawn / early termination subjects will also be included in this analysis.

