13.5 Analysis by Subject Disposition

The number of subjects that are enrolled, excluded, discontinued, prematurely withdrawn from the study, and lost to follow-up will be summarized and listed by randomization group, by gender, and by study site.

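### Section 9.6 makes ineligible subjects non-evaluable without stopping at randomization, which read literally conflicts with the intent-to-treat analysis in 13.4

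*Combined protocol and SAP*

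**What the plan says.** Section 9.6 sorts subjects under two headings, Evaluable and Non-Evaluable. The second has one entry, Excluded: "Subjects found to not meet one of the study inclusion/exclusion criteria after the being enrolled". Section 9.2 fixes when enrollment occurs: "Patients who sign the informed consent form will be considered enrolled in the study". Randomized subjects are a later subset, each a "subject who remain free from arrhythmia recurrence after signing the study ICF and are randomized into one of the study arms".

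For withdrawn subjects 9.6 adds that "they will remain in the analysis cohort until the time at which they are withdrawn", and it has a parallel sentence for discontinued subjects. It has none for excluded subjects.

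Section 13.4 sets the analysis population: "The primary analysis will be based on the intent-to-treat principle where subjects will be analyzed by the group to which they are randomized". It then adds: "Lost-to-follow-up, discontinued, and withdrawn / early termination subjects will also be included in this analysis". Excluded subjects are not mentioned. The censoring rule in 13.7.1 covers lost, withdrawn and discontinued subjects and is also silent on excluded ones.

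Section 13.5 plans the disposition table: "The number of subjects that are enrolled, excluded, discontinued, prematurely withdrawn from the study, and lost to follow-up will be summarized and listed by randomization". The breakdown is thus by arm, with further splits by gender and site.

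**The concern.** An intent-to-treat analysis keeps every randomized subject, whatever is later learned about eligibility. Section 9.6 as worded provides a class of subjects who do not count, and its only boundary is consent, so it stays open through the 12-month Evaluation Period. Anyone applying 9.6 to a randomized subject later found ineligible would have a textual basis for leaving that subject out.

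Three features of the trial make this more than a drafting matter. It is unblinded (8.1). Some exclusion criteria in 9.4 rest on judgement: number 7 turns on the investigator's opinion, and number 16 on ability or willingness to comply, which can look different after randomization. And no section says who decides that a subject is excluded, by when, or without knowledge of arm and outcome. With few primary events expected, a single such decision can visibly shift an arm's event rate.

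**Working it through.** **Text check.** The plan has no figure to reproduce on this point, so the main check sets the sections side by side.

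1. When does the Excluded class open? At consent (9.2).
2. When does it close? Section 9.6 gives no end. Randomization comes later (9.5) and is not named as a limit.
3. Is an excluded subject kept in the analysis? In 9.6 the heading says non-evaluable, and the sentence that keeps withdrawn and discontinued subjects in the cohort is absent. In 13.4 the first sentence would keep anyone randomized; the list that follows omits this class.
4. Does 13.5 show that excluded subjects can have a randomized group? No. The same sentence tabulates enrolled subjects by randomization group, and enrolled subjects include those who consent, fail the pre-randomization monitoring and never receive a group. The phrase is applied to the whole disposition list and does not discriminate between the readings.

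Two readings therefore remain open. Under the narrow one, all 100 randomized subjects are analysed. Under the literal one, fewer may be.

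**Size, for illustration.** Inputs: 50 subjects per arm (13.3). The documents give no expected event rate for this post-ablation population. Section 5.1 gives a background stroke rate without antithrombotic therapy of fewer than 2 to more than 10 per 100 patient-years, so I assume 12-month primary event rates of 1% to 10%.

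Expected events per arm = 50 × p; chance of at least one = 1 − (1 − p)^50:

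| Assumed p | Expected events | Chance of at least one |
|---|---|---|
| 1% | 0.5 | 0.40 |
| 2% | 1.0 | 0.64 |
| 5% | 2.5 | 0.92 |
| 10% | 5.0 | above 0.99 |

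Excluding one subject with an event changes x/50 to (x − 1)/49. The fall is (50 − x)/(50 × 49):

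- x = 1: 1/50 = 2.0% becomes 0/49 = 0%; the arm's only event is gone.
- x = 2: 2/50 = 4.0% (exact 95% interval 0.5% to 13.7%) becomes 1/49 = 2.0% (0.1% to 10.9%). Fall = 48/2450 = 1.96 points, about half the estimate.
- x = 5: 5/50 = 10.0% becomes 4/49 = 8.2%. Fall = 45/2450 = 1.84 points.

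So over 1 to 5 events, one exclusion lowers the arm's proportion by about 2 points and removes 1/x of its events, from 100% down to 20%.

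The Fisher test named in 13.7.1 is less sensitive. With no events in the other arm, 2/50 gives p = 0.49, and 1/49 also gives p = 0.49. It takes an example such as 6/50 against 0/50 (p = 0.027), with two event subjects excluded from the same arm (4/48 against 0/50, p = 0.054), to cross 0.05.

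**The case against.** The strongest reply is that Excluded was meant only for subjects who consent and then fail before randomization. The sequence in 9.2 supports this: consent, then monitoring, then randomization of those who qualify. Table 3 schedules the eligibility review at screening and at baseline only, with none in the Evaluation Period. Consented subjects who fail need a category, and Excluded is the only one in 9.6 that fits them. On this reading 13.4 has no reason to name them, its opening sentence already keeps everyone randomized, and its list adds to that set without closing it. The 9.6 headings are loose in any case, since Evaluable includes everyone who signed the consent form, and Section 13 never uses evaluability to define an analysis set.

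Most of this stands. It makes the narrow reading plausible, perhaps the likelier intention. It does not put a limit into 9.6, and a reader with only the text cannot tell which reading governs.

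A reader might go further and infer from 13.5 that the plan foresees exclusion after randomization. The documents do not support that, for the reason in step 4 of the check. Nor would events vanish from the record: Section 12.5 requires adverse events to be recorded from consent to study end, serious ones go to the safety committee, and 13.5 counts and lists excluded subjects. What is exposed is the analysis set.

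**Conclusion.** The point holds as a conflict on the literal wording. Section 9.6 labels as non-evaluable a class that can include randomized subjects, while 13.4 promises an analysis by randomized group and does not say what happens to that class. The documents permit removal of randomized subjects; they do not order it. The stronger statement, that the plan directs such removal or plainly contradicts intent-to-treat, is not supported while the narrow reading is available.

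The size rests on assumed event counts: about 2 percentage points of an arm's event proportion for each event subject excluded, for example 4.0% to 2.0%. Section 13.3 says the pilot is not powered for inference, and no non-inferiority margin is given, so there is no powered conclusion to overturn. The exposure is in the event proportions, the Kaplan-Meier estimates and the exploratory tests. These still matter, because the non-inferiority objective in 13.1 has nothing else to draw on. It should be corrected, with moderate confidence about the effect and high confidence that the wording is open.

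**What to change.** - **Section 9.6:** limit Excluded / Non-Evaluable to subjects who fail eligibility after consent and before randomization.
- **Section 13.4:** state that every randomized subject is analysed in the randomized group, including any later found ineligible. The censoring rule in 13.7.1 then applies to them as to anyone else.
- **Optional:** an analysis restricted to eligible subjects may be added as a prespecified sensitivity analysis, with ineligibility decided without knowledge of arm or outcome.

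The first two changes are one sentence each. They need no extra subjects, visits or data, and they leave the sample size of 100 unchanged.

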9.7 Subject Withdrawal

The investigator may remove a subject from the study for any of the following reasons: withdrawal is in the subject's best interest, subject preference, concurrent illness, noncompliance, or any other situation the investigator deems a compromise to the integrity of the study. Subjects will be informed prior to study entry that they are free to withdraw from the study at any time and for any reason, without prejudice to his or her future medical care by the physician or the institution.

If a subject is removed from the study, the date and reason for withdrawal will be recorded on the appropriate electronic case report form (eCRF). If the subject is withdrawn due to an adverse event (AE) or serious adverse event (SAE), the Investigator must comply with all reporting requirements described in Section 12 and must follow the subject until the AE/SAE has resolved or stabilized.

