Although the efficacy of warfarin in preventing stroke in AF patients has been clearly demonstrated, oral anticoagulation is still underused in clinical practice for several reasons. Firstly, oral anticoagulation therapy carries a substantial risk of hemorrhage; this could be underestimated in clinical practice, considering the restrictive selection criteria used in randomized trials, in which patients with lower risk of bleeding are often enrolled. For example, in the SPINAF trial only 7% of the 7982 patients initially screened were enrolled.¹⁰ Moreover, the risk of hemorrhage is strictly related to the patient's age. Indeed, the incidence rate of major hemorrhage has been found to rise from 1.5 per 100 patient-years for patients younger than 60 years to 4.2 per 100 patients-years for patients older than 80 years (hazard ratio of 2.7).¹¹ In a meta-analysis of major randomized trials of oral anticoagulation therapy, the mean age of patients was 69 years, and only 20% of participants were older than 75 years.⁹

By contrast, in clinical practice this latter group of patients represents more than 50% of the population that needs to be treated with anticoagulation therapy.⁷ The second reason for the underuse of oral anticoagulation is that this therapy, specifically warfarin, is associated with restrictions in everyday life, as it requires frequent monitoring of the INR level in order to adjust the therapeutic dosage. Finally, it is well known that a considerable percentage of patients are unable to comply with oral anticoagulation therapy. In warfarin-treated patients, discontinuation of this therapy occurs at rates of up to 38% a year and approximately 50% of strokes occur during inadvertent therapeutic lapses or in subjects who temporarily or permanently cease therapy.⁸

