13.7 Endpoint Analyses

13.7.1 Primary Endpoint Analysis

The primary endpoint is the occurrence of any thromboembolic event or major hemorrhagic complications during the 12-month Evaluation Period.

The Kaplan-Meier method will be used to model the time to the first occurrence of any thromboembolic event or major hemorrhagic complications during the 12-month Evaluation Period following randomization. The survival probabilities of the occurrence of any thromboembolic event or major hemorrhagic complications at the 12 month follow-up along with the corresponding 95% confidence intervals will also be presented. The equality of the survival curves between two randomization groups will be tested by the Log-rank test.

This analysis will include all subjects in the analysis population and account for censored observations. Subjects lost to follow-up, withdrew or discontinued prior to reaching their primary endpoint will be censored at their last visit.

Descriptive statistics such as 25th percentile, median and 75th percentile of time to the first occurrence as well as the 95% confidence intervals around the median time will be presented overall and by randomization groups.

The number and proportion of subjects experiencing occurrence of any thromboembolic event or major hemorrhagic complications will be summarized overall and by two randomization groups at 12 month follow up. The Fisher exact test will be used to compare the proportions between the two randomization groups.

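### Section 9.7 lets an unblinded investigator end a subject's outcome follow-up for noncompliance, illness or preference, which defeats the intent-to-treat aim of 13.4 in effect and probably makes the censoring informative

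*Combined protocol and SAP*

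**What the plan says.** Section 9.7 gives the investigator discretion to remove a subject from the study. Besides the subject's best interest, the grounds are "subject preference, concurrent illness, noncompliance, or any other situation the investigator deems a compromise to the integrity of the study". Section 8.1 describes the trial as unblinded.

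Section 9.6 sets the consequence: "Withdrawn subjects are exited from the study prior to completion of all follow-up visits", although "they will remain in the analysis cohort until the time at which they are withdrawn". The only later follow-up that 9.7 requires is after withdrawal for an adverse event, when the investigator "must follow the subject until the AE/SAE has resolved or stabilized".

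Section 13.4 makes the primary analysis intent-to-treat: "subjects will be analyzed by the group to which they are randomized, regardless of actual treatment received". It adds: "Lost-to-follow-up, discontinued, and withdrawn / early termination subjects will also be included in this analysis". Section 13.7.1 sets the censoring rule: "Subjects lost to follow-up, withdrew or discontinued prior to reaching their primary endpoint will be censored at their last visit". It specifies a log-rank test on time to first event and a Fisher exact test on the 12-month proportions.

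Sections 11.2.1 and 11.3 require test subjects who resume OAT to leave the study. No section gives a corresponding rule for control subjects who stop OAT.

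**The concern.** Section 9.7 does not distinguish stopping or changing the assigned strategy from ending outcome follow-up. A subject who stops complying, falls ill or prefers the other strategy can lose both at once. The person deciding knows the arm and has just seen behaviour or illness that may predict stroke or bleeding. Censoring that follows such a decision is unlikely to be independent of the outcome, as Kaplan-Meier and the log-rank test require.

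An intent-to-treat analysis needs outcomes after departure from assigned treatment. Keeping the subject in the analysis set does not supply them.

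Controls who stop OAT are a particular case. With no rule of their own, they could be removed as noncompliant at one site and kept at another, so the control arm's observed risk would depend partly on local habit. Section 5.1 gives a reason to care about these periods. In warfarin-treated patients, it says, "discontinuation of this therapy occurs at rates of up to 38% a year and approximately 50% of strokes occur during inadvertent therapeutic lapses"; the sentence goes on to include patients who temporarily or permanently stop.

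**Working it through.** **Plan's own figure.** Section 13.3 gives 100 subjects, 50 + 50, with no alpha, power, margin, event rate or dropout assumption. There is no calculation to reproduce, so the check is how much control-arm follow-up the clause could cost.

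**Inputs from the documents.** 50 controls (13.3); 12 months of follow-up (10.1); in warfarin patients, discontinuation of up to 38% a year and about 50% of strokes in lapses or after cessation (5.1); 1.2% a year added major bleeding on warfarin (5.1); visits at 3, 6 and 12 months (Table 3).

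**Assumptions.** Discontinuation of 10% and 20% a year as lower alternatives; a constant rate of stopping; stopping is permanent; a share f of off-OAT time, with the strokes in it, is lost through removal; control stroke rates of 1%, 2% and 4% a year.

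**Person-time.** For annual discontinuation d, the hazard is h = -ln(1 - d), and mean time on OAT in one year is (1 - exp(-h))/h = d/h. At d = 0.38, h = 0.478 and d/h = 0.38/0.478 = 0.795. The off-OAT share is 0.205, and 50 × 0.205 = 10.3 person-years.

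| d per year | Controls stopping (50 × d) | Off-OAT share | Person-years of 50 |
|---|---|---|---|
| 10% (assumed) | 5 | 5.1% | 2.5 |
| 20% (assumed) | 10 | 10.4% | 5.2 |
| 38% (5.1, upper figure) | 19 | 20.5% | 10.3 |

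**Stroke rate.** If half of control strokes fall in off-OAT time, the observed rate relative to full follow-up is (1 - 0.5f)/(1 - 0.205f) at d = 0.38:
- f = 0.25: 0.875/0.949 = 0.92
- f = 0.5: 0.75/0.897 = 0.84
- f = 1: 0.5/0.795 = 0.63

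At f = 1 the ratio is 0.53 for d = 10% and 0.56 for d = 20%. Those two are less credible: putting half of all strokes into 5% or 10% of the time implies off-to-on stroke rate ratios of about 19 and 9, against about 4 at 38%.

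**Counts.** At 1%, 2% and 4% a year, 50 controls have 0.5, 1.0 and 2.0 expected strokes. At f = 1, half are unobserved: 0.25, 0.5 and 1.0.

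**Bleeding.** With lapsed time followed, the added bleeding averages 1.2 × 0.795 = 0.95 per 100 person-years. With it removed, the figure is 1.2, a rise of 0.25. At d = 0.38, f = 1 and a stroke rate of 1% a year, the stroke component falls from 1.00 to 0.63, a drop of 0.37. The two components move in opposite directions.

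**Censoring date.** Section 9.6 counts a subject until withdrawal; 13.7.1 censors at the last visit. With visits at 6 and 12 months the gap can approach 6 months.

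**Fisher test.** It takes no account of shortened follow-up. A subject removed early without an event counts as event-free if kept in the denominator.

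**The case against.** The strongest defence is that nothing here contradicts the intent-to-treat rule and nobody is deleted. A reader of 9.7 beside 13.4 might infer both, but the documents do not support it. Section 13.4 expressly includes withdrawn subjects, 9.6 keeps them in the cohort up to withdrawal, and 13.7.1 censors them, so earlier events and time count. This stands. The conflict is one of effect.

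Follow-up also does not always stop at exit. The definition of an adverse event in 12.1 is broad enough that a new concurrent illness will normally be one, and an adverse event that leads to withdrawal must be followed. If the illness is itself a stroke or major bleed, the endpoint has already been reached. This stands too: what is at risk is later, separate events.

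The clause says the investigator may remove, noncompliance is undefined, and it could mean missed visits. Treating a control who stops OAT as noncompliant is an inference. That is fair, but the lack of any rule is what permits sites to differ.

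A reader might also infer that half of control strokes would go uncounted. That would need every lapse to be detected and the subject removed before the stroke. Section 5.1 speaks of inadvertent lapses and visits are months apart, so many such strokes would occur while the subject was still in the study, and would be counted. The 38% and 50% figures describe warfarin patients in general. These subjects are ablated, free of AF recurrence, already on anticoagulation for at least two months, and may take any approved OAT.

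Finally, the mandatory exits in 9.6, 11.2.1 and 11.3 threaten intent-to-treat follow-up more than this discretionary clause. That is correct and shapes the fix, but correcting those exits alone would leave 9.7 open.

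**Conclusion.** The concern holds as a defect of outcome follow-up. Discretionary removal by an unblinded investigator ends observation of the primary endpoint, so events after departure from the assigned strategy are missed and the censoring is probably informative. The 19 of 50 controls and 20% of control person-time are an upper illustration, resting on a general warfarin figure, permanent stopping and removal of everyone who stops. The lower figures rest on assumed rates.

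The number of strokes missed cannot be fixed from the documents, because it depends on how many lapses are found and lead to removal before the event. A reader might conclude that the clause flatters the control arm. On stroke alone it could, but losing off-OAT time tends to raise the control bleeding rate, and removals for illness in either arm are not quantified here. The net direction on the composite is unclear.

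Section 13.3 states that the pilot is not powered for inference. The damage is therefore to its safety estimates and to the design of a later trial, not to a confirmatory test. With so few expected events, one missed stroke would still be visible in the estimates. The change should be made.

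**What to change.** 1. In 9.6 and 9.7, separate stopping or changing the assigned strategy from ending outcome follow-up. End outcome collection only for withdrawal of consent to follow-up, death or true loss to follow-up.
2. For every other reason, including removal in the subject's best interest, record the date and reason. Collect stroke, major bleeding and death to month 12 at the existing visits, or by telephone or record check, and count those events in the 13.4 analysis.
3. Apply the same outcome-collection rule to the exits in 9.6, 11.2.1 and 11.3, without altering any treatment rule. Amending 9.7 alone would have controls off OAT followed to month 12 while test subjects who resume OAT leave, which adds asymmetry between the arms.
4. Reconcile the censoring date between 9.6 and 13.7.1.
5. Report a supportive on-treatment analysis beside the intent-to-treat result, because lapsed controls who are retained dilute a difference in the non-inferiority question posed in 13.1. Medication changes are already recorded under 11.4.2, and start and stop dates are required in source documents under 14.7.3.

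The cost is an amendment to the wording, somewhat more follow-up on the existing schedule and one extra analysis. Outcomes not collected during the trial may not be recoverable at analysis.
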